## 5 Study Methods

### 5.1 General Study Design and Plan

This is a randomized, pragmatic QI study designed to evaluate the effectiveness of proactive panel management to close gaps in evidence-based care for patients with HFrEF. We will use the VA's ADHFD to generate a list of actionable patients with HFrEF and left ventricular ejection fraction (LVEF)  $\leq 35\%$ . After identifying a cohort of HFrEF patients from the ADHFD, we will randomize individual patients on the actionable list to usual VA care or a novel proactive panel management clinic. Clinicians will be trained on how to use the dashboard information to identify opportunities for optimization based on detailed chart review. The proactive panel management intervention will use clinicians to perform an electronic chart review and call patients impromptu at their discretion to evaluate HFrEF management and opportunities to optimize GDMT. Each panel management clinic is staffed by a single cardiovascular clinician or trainee with cardiology (PI) supervision. All patients will receive chart review or telehealth notes brought to the attention of primary care and cardiology clinicians. Patients randomized to the intervention will only receive one chart review during a half-day panel management clinic with follow-up of any laboratory results or diagnostic tests as required and referral to HF or general cardiology clinic as deemed appropriate. The control arm consists of the usual delivery of health services with routine scheduled appointments for primary care or cardiology.

Outcomes will be assessed at 6-months from the last patient to receive the intervention. The study is powered to detect superiority of the intervention compared to usual care in optimizing GDMT for HFrEF. Treatment assignment is based on 1:1 randomization using fixed blocks (size=6) to assure an equivalent number of patients randomized to the intervention and usual care. Patients are randomized after a list of 300 actionable patients are generated from the ADHFD. Study participant numbers will be assigned to the list of patients sorted by optimization scores in Excel. The supervising statistician (AA) will generate concealed randomization assignments by participant identification numbers. The randomization assignments will be merged with baseline study dataset and exported as password protected Excel and PDF documents. Study investigators will divide the intervention arm into lists of 10 to 15 per half-day clinic. Patients not receiving chart review or phone call attempts will be reassigned to future panel management clinics until all patients receive the intervention. Patients that did not answer phone calls will receive chart review notes for primary care and cardiology clinicians and not be reassigned to future panel management clinics.

Study participants do not require informed consent as determined by the VA IRB review. Patients will receive all accepted standards of care and medications approved by the Food and Drug Administration for HFrEF indications. The VA Subcommittee for Research and Safety found an absence of any declared research-laboratory-based biohazards and granted exemption from continued review. The study will evaluate the effectiveness of the QI intervention, telephone/telemedicine panel management clinics, to more rapidly implement evidence-based care for patients with HFrEF. Patients in the usual care arm will be unaware they are part of the control group for the RCT. Intervention patients nor study staff are blinded to usual care or intervention assignments. Patients that receive the intervention will be informed this is a pilot quality improvement effort with informal consent before proceeding to the clinical interventions. Intervention patients may refuse to participate after being contacted by phone in the intervention.

Study enrollment is based on the inclusion and exclusion criteria used to filter the ADHFD list. A list of actionable patients with HFrEF will be exported for randomization. The GDMT optimization score will be automated for each patient on the extracted list (**Table 1**). A sample of 300 patients will be selected with the lowest GDMT composite scores. Once the final sample of the study is determined, patients will be randomized to usual care or the intervention. Intervention patients will be divided into smaller lists of 10 to 15 patients. These smaller

lists will be assigned to proactive panel management clinics. Clinicians staffing the intervention clinics will review ADHFD data, review the electronic health record (EHR) and decide whether to proceed to evaluate and recommend treatment over the phone to patients directly. If clinicians did not have sufficient time to review all patients on their clinic list, they will be redistributed to future intervention clinics. Intervention clinics will be held until each patient assigned the intervention has a chart review or attempted telephone contact. A failure to contact a patient will trigger a letter to a patient or electronic communication to their primary care or cardiology clinician.

Prior to each ADHFD telehealth clinic (half-day clinic lasting 4 to 4.5 hours), clinicians will be sent a secure email that will include a password-protected Excel document of 15 patients with exported clinical summary data from the ADHFD. Clinicians will be instructed to chart-review patients and decide if an opportunity exists to further optimize the receipt of GDMT. Clinicians will also be given a document providing guidance on the sequence of GDMT optimization based on latest guidelines and VA policies (Supplement S1 GDMT Guidance Document). If a patient does not qualify for further optimization (i.e. chart documentation of prior intolerance, patient preference), a short note in the electronic health record (EHR) will document the chart review and inform the primary care clinician that based on chart review, no opportunity currently exists but they may consider further GDMT titration in the future. If a patient appears to have an opportunity for further titration, the clinician is encouraged to call the patient to see if they are available to discuss their HF care. If the patient agrees, a telehealth visit will take place over phone or switch to video. A formal telehealth cardiology visit will occur at the time of care. If the patient is interested but does not have time for a visit, a brief telephone note will be placed and a request for a future cardiology clinic visit will be requested. If a formal telehealth visit occurs, clinicians will be asked to inquire about key details around medication titration (**Supplement S2 Interview Guide**). The data from chart review and interviews will be documented on a password-protected Excel document (**Supplement S3 Clinician Documentation Form**). Any medication addition or titration will have indicated laboratory labs ordered per usual care. Lastly, clinicians will also be asked to administer a short survey with each participant based on a template at the end of the call proactive phone call (**Supplement S2 Interview guide**). Primary care and regular cardiology clinicians will be notified of any changes in medication management in the EHR. The study's lead (BZ, AV) will be available by phone to answer questions or problems that arise during the clinic. Supervision of patient encounters by clinical pharmacists, medical trainees, or advanced practice nurse practitioners and study protocols will be BZ as the licensed and boarded general cardiologist.

## **5.2 Inclusion-Exclusion Criteria and General Study Population**

This quality improvement (QI) initiative involves patients with heart failure with reduced ejection fraction (HFrEF) receiving care in the VA West Los Angeles (WLA). The criteria for eligible patients are:

### **Inclusion criteria:**

- Facility: Greater Los Angeles, CA
- Division: All divisions within Greater Los Angeles
- Patient is eighteen years of age or older
- Patients has a primary diagnosis of HFrEF (last documented LVEF  $\leq 35\%$  per ADHFD algorithms)
- Patient has an estimated GFR greater than or equal to 30 mL/min
- Patient lacks at least one active prescription of a beta-blocker, ACE/ARB/ARNI, MRA, or SGLT2i
- There are no cardiology appointments in the upcoming 2 weeks.

### **Exclusion criteria:**

- Patient is currently hospitalized at WLA

### **5.3 Randomization and Blinding**

Patients will be randomized 1:1 to intervention and usual care groups with all patients randomized at one time; given the target sample size of n=300 total patients, the sequence will be generated using permuted blocks of size 6 to ensure that an equal number of patients are randomized to panel management and usual care, maximizing efficiency (power). The randomization sequence will be concealed from the clinicians until after randomization has already been complete. Post-randomization, study staff will not be blinded to allocation. GLA IRB exemption was granted for consent of the low risk, non-experimental intervention. The intervention does not allow for blinding of participants in the intervention arm.

### **5.4 Study Assessments**

Data for analysis will be pragmatically ascertained through the variables available in the ADHFD. The ADHFD data will be exported at baseline. To evaluate study outcomes, the ADHFD will be exported again to a secure Excel file 6-months after the last participant receives the intervention. The ADHFD data includes age, race, hospitalization risk scores, number of VA hospitalizations in the past 12 months, vital signs (weight, blood pressure, pulse), laboratory values (potassium, creatinine, BNP, eGFR), active GDMT prescriptions, and upcoming appointments. Sem-structured survey data will be captured by clinicians for only intervention patients. No interim analyses are planned. Longer term secondary evaluations will be evaluated at 1 and 2 year.

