## **4 Study Objectives and Endpoints**

### **4.1 Study Objectives**

The purpose of this study is to measure the effectiveness of proactive panel management clinics to optimize GDMT relative to usual care. The study will also evaluate secondary outcomes that signify improved outcomes such as reduced hospitalizations and mortality. The study will also evaluate clinician time per intervention relative to usual cardiology or HF clinic structure.

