### 4.2.2 Secondary outcome

The secondary outcomes of the study will include the following at final evaluation:

1. Active prescriptions for individual classes of GDMT
  - a. ACE/ARB/ARNI
  - b. Beta-Blocker
  - c. MRA
  - d. ARNI
  - e. SGTL2i
2. Hospitalizations
  - a. Total number of any cause hospitalization
  - b. Total number of primary HF hospitalizations
  - c. Proportion of patients with any hospitalization
  - d. Proportion of patients with any HF hospitalization
3. Number of deaths
4. Clinician time spent per patient from opening chart to end of patient-specific intervention and documentation.
5. Health service efficiency
  - a. Number of patients reviewed or contacted per half-day clinic
  - b. Number of medication adjustments (stop, start, titration) per half-day clinic
  - c. Number of laboratory tests ordered per half-day clinic
  - d. Number of imaging/diagnostic procedures ordered per half-day clinic
  - e. Number of referrals for consults/device therapy per half-day clinic
6. Qualitative evaluation of patient surveys who received the intervention.

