## **7 General Analysis Considerations**

### **7.1 Timing of Analysis**

The final analysis will be performed at 6 months after the last participant received the study intervention. For patients, who are no longer captured by the ADHFD at this time, study staff will abstract relevant data based on chart review.

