### **7.2 Analysis Populations**

All subjects randomized per intention to treat. Any deaths, hospitalizations that occur prior to receipt of the intervention will be included in the primary analysis.

Secondary outcomes assessment will evaluate patients that received the telephone intervention vs. did not receive any protocolized interventions.

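### The start of hospitalization follow-up is only implied, and the one hospitalization count listed from the dashboard looks back 12 months, which does not match follow-up from randomization unless roll-out takes about 6 months

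*SAP*

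**What the plan says.** SAP 4.1 sets the objective: "The study will also evaluate secondary outcomes that signify improved outcomes such as reduced hospitalizations and mortality". SAP 4.2.2 lists four hospitalization outcomes at the final evaluation: the any-cause count (2a, "Total number of any cause hospitalization"), the count of primary HF admissions (2b), and the proportions with any admission (2c) and any HF admission (2d). SAP 9.2 adds a hazard ratio for HF hospitalization and gives it no time origin.

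**Source.** SAP 5.4 draws analysis data from ADHFD variables, and for outcomes "the ADHFD will be exported again to a secure Excel file 6-months after the last participant receives the intervention". SAP 10.1 also takes HF hospitalizations from the dashboard at study end. The one hospitalization count in the SAP 5.4 list is "number of VA hospitalizations in the past 12 months". Table 2 (SAP 8.4) repeats the 12-month span in a row labelled as HF hospitalizations but described as counting any VA admission. The other admission-related fields are a hospitalization risk and rank, the date of the last HF discharge, current inpatient status and a recent ED visit.

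**Timing.** Under SAP 5.3 the trial proceeds "with all patients randomized at one time". Delivery is staggered: "Study investigators will divide the intervention arm into lists of 10 to 15 per half-day clinic" (SAP 5.1). SAP 7.2 specifies intention to treat and adds: "Any deaths, hospitalizations that occur prior to receipt of the intervention will be included in the primary analysis". SAP 3.1 describes the observation period simply as 6 months.

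**Fallback.** SAP 7.1: "For patients, who are no longer captured by the ADHFD at this time, study staff will abstract relevant data based on chart review". SAP 8.1 and 10.1 likewise tie chart review to patients missing from the dashboard. SAP 7.4 is broader and covers data missing from the dashboard that an analysis needs.

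**The concern.** An outcome export taken on one calendar date, with a count that looks back a fixed 12 months, does not measure events since randomization. It does so only if randomization happened 12 months before the export. Because export is set at 6 months after the last intervention, that requires a roll-out of about 6 months, and the plan does not fix the length of roll-out.

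Admissions before randomization cannot be affected by the intervention. Including them pulls the comparison toward no difference. If roll-out is longer than 6 months, the count instead loses the first weeks of follow-up. Chart-reviewed patients might be counted over a different interval from those still on the dashboard, which would mix two windows within one outcome.

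The contradictory Table 2 row adds a second difficulty: an analyst cannot tell which outcome the field could serve. At stake are the secondary hospitalization outcomes named in the objectives.

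**Working it through.** The plan gives no figure for the hospitalization window, so there is none to reproduce. Its one design calculation (83% power, SAP 6) concerns the medication score and does not enter here.

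**Inputs from the documents.** 300 patients randomized 1:1, so 150 in the intervention arm; lists of 10 to 15 per clinic; export 6 months after the last intervention; 12-month look-back.

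**Assumptions.** Clinic frequency (not stated, so a range is shown); a true rate ratio of 0.70 from randomization; constant admission rates, equal in the two arms before randomization; 4.348 weeks per month.

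**Step 1, roll-out.** Clinics needed: 150/15 = 10 to 150/10 = 15. From the first to the last of n clinics is n-1 intervals; allowing for a lag before the first gives n. Roll-out R = intervals × weeks between clinics / 4.348.

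**Step 2, follow-up and overlap.** Follow-up F = 6 + R months. Share of the look-back before randomization f = max(0, (12 - F)/12). Observed rate ratio = 0.70(1 - f) + f.

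| Clinic schedule | R (months) | F (months) | f | 0.70 appears as |
|---|---|---|---|---|
| Twice weekly, 10-15 clinics | 1.04-1.72 | 7.04-7.72 | 41-36% | 0.82-0.81 |
| Weekly, 10-15 clinics | 2.07-3.45 | 8.07-9.45 | 33-21% | 0.80-0.76 |
| Every two weeks, 10 clinics | 4.14-4.60 | 10.14-10.60 | 16-12% | 0.747-0.735 |
| Every two weeks, 15 clinics | 6.44-6.90 | 12.44-12.90 | 0 | 0.70, with follow-up lost |

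Weekly example, 10 clinics and 9 intervals: R = 9/4.348 = 2.07; F = 8.07; f = 3.93/12 = 0.328; 0.70 × 0.672 + 0.328 = 0.798. In the last row the count misses F - 12 = 0.44 to 0.90 month, which is 3.5% to 7.0% of F. An exact match needs R = 6 months, or 6 × 4.348 = about 26 weekly intervals.

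**Step 3, the proportion 2c, if the field counts any admission.** Let p be the 12-month control risk and h = -ln(1 - p)/12. The risk ratio over true follow-up is (1 - exp(-0.7hF))/(1 - exp(-hF)). Over the look-back it is (1 - exp(-h(12 - F) - 0.7hF))/p. With weekly clinics and an assumed p = 0.30, h = 0.0297. At F = 8.07 a ratio of 0.725 appears as 0.826; at F = 9.45, 0.729 appears as 0.795. Over p from 0.20 to 0.50, true ratios of about 0.72-0.755 appear as 0.78-0.85.

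**Step 4, which outcomes have a source.**
- If the field counts any VA admission, it could supply 2a and 2c with the mismatch above; 2b has no listed source.
- If it counts HF admissions, it could supply 2b with the mismatch; 2a and 2c have no listed source.
- 2d can largely be recovered under either reading, from the last HF discharge date plus inpatient status.
- The hazard ratio needs the first HF admission after randomization. A last discharge date does not give that.

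**The case against.** A reader might infer that the SAP leaves the window wholly undefined, that the 12-month count is the declared outcome variable, and that 2a, 2b and 2c would all be diluted. The documents support none of these.

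- **The window is partly defined.** Its end is given in SAP 4.2.2, 5.4 and 7.1. Intention to treat and the SAP 7.2 sentence on events before the intervention point to a start at randomization. That sentence is worded for the primary analysis, whose outcome is a prescription score containing no hospitalizations, so it may be a counting rule or may only mean that such patients are retained.
- **The field is not assigned to an outcome.** SAP 5.4 lists dashboard contents without mapping them to endpoints, and Tables 2 and 3 present the count as a baseline variable. The mismatch is therefore conditional. But if the field is baseline only, no listed variable supplies 2a, 2b or 2c.
- **One field cannot dilute all three.** It counts either any admission or HF admissions.
- **Chart review may help.** SAP 7.4 is not limited to patients who left the dashboard, and the hazard ratio already requires dated events. Still, a populated 12-month count need not be treated as missing, and three other sections restrict chart review to patients off the dashboard.
- **The size rests on assumptions.** Redistributing unreviewed patients lengthens roll-out and shrinks the pre-randomization share. If the effect begins only at receipt, with a mean wait of R/2, then under weekly clinics the correctly windowed ratio is already (R/2 + 0.70(F - R/2))/F = 0.74-0.755. The look-back shows (12 - 0.30(F - R/2))/12 = 0.82-0.81. The added dilution is then about 0.05-0.09, against 0.06-0.10 in the main calculation.
- **These are unpowered secondary outcomes**, and SAP 9.2 specifies no test for 2a-2c. That limits the weight of the point but does not remove it, since reduced hospitalization is a stated aim.

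**Conclusion.** The point holds in a limited form. The end of hospitalization follow-up is stated and the start is implied. The stated source, one dashboard export, lists a single count whose 12-month span agrees with follow-up from randomization only if roll-out takes about 6 months.

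If that count is used, weekly clinics would place about 21-33% of the window before randomization and turn an assumed rate ratio of 0.70 into about 0.76-0.80. A roll-out beyond 6 months would lose early follow-up instead. The mismatch falls on 2a and 2c or on 2b, not on all three, and whatever the field does not cover has no listed source. The lack of a first-event time for the hazard ratio does not depend on any of these assumptions.

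Admissions before randomization are balanced between arms in expectation. The consequence is dilution and noise, not an advantage to either arm, and the primary medication-score analysis is untouched. The plan should be corrected before the outcome export, but the point does not threaten the trial's main result.

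**What to change.** In SAP 5.4, 9.2 and 10.1:

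- Define each hospitalization outcome as admissions dated from randomization to the final export date.
- Take admission dates and principal diagnosis from the VA record for all 300 randomized patients, by the same rule in both arms and whether or not the patient is still on the dashboard.
- Time the hazard ratio from randomization to first HF admission.
- Keep the 12-month field as a baseline characteristic only, as in Table 3.
- Reconcile the label and description of the Table 2 row.

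Settle this before the outcome export: study staff are not blinded to allocation (SAP 5.3), and a window chosen afterwards could depend on the data.

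The cost is a few lines of SAP text and one record query, or a short chart check, for 300 patients. The SAP already plans chart review and use of VA pharmacy data.

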## **6 Sample Size**

Assuming a baseline average GDMT optimization score of 2.4 for the included population and a standard deviation of 1.5, we estimate a sample of 300 patients to have 83% power to detect 25% improvement in GDMT optimization scores for the intervention (standard deviation assumed 1.9 for the intervention arm). The primary analysis will be performed using ANCOVA with baseline adjustment for age which should improve the power to detect a difference between treatment arms.

## **7 General Analysis Considerations**

### **7.1 Timing of Analysis**

The final analysis will be performed at 6 months after the last participant received the study intervention. For patients, who are no longer captured by the ADHFD at this time, study staff will abstract relevant data based on chart review.

### **7.2 Analysis Populations**

All subjects randomized per intention to treat. Any deaths, hospitalizations that occur prior to receipt of the intervention will be included in the primary analysis.

Secondary outcomes assessment will evaluate patients that received the telephone intervention vs. did not receive any protocolized interventions.

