## 9 Efficacy Analysis

The analysis will evaluate differences between usual care and the intervention arm (intention to treat) in the receipt of active prescriptions for GDMT, hospitalizations, and mortality.

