## 9.2 Secondary Efficacy Analysis

The secondary efficacy analysis will include the difference in OPS score 6-months after the last intervention using an unadjusted parametric ANCOVA.

Additional secondary analyses include:

- Difference in rates of receipt of each class of GDMT using a two-sample proportions test Pearson's chi-squared test between intervention and usual care assignment.
  - ACE/ARB/ARNI
  - ARNI
  - Beta-blocker
  - MRA
  - SGLT2i
- Hazard ratio for heart failure hospitalization at final evaluation between intervention.

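### SAP 7.2 sets an unlabelled by-receipt comparison for the secondary outcomes, in conflict with the intention-to-treat comparison in SAP 9 and 9.2

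*SAP*

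**What the plan says.** SAP 7.2 (Analysis Populations) has two short paragraphs.

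- The first reads "All subjects randomized per intention to treat" and continues "Any deaths, hospitalizations that occur prior to receipt of the intervention will be included in the primary analysis".
- The second reads "Secondary outcomes assessment will evaluate patients that received the telephone intervention vs. did not receive any protocolized interventions".

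SAP 4.2.2 lists GDMT classes, hospitalizations (for example "Total number of any cause hospitalization") and "Number of deaths" as secondary outcomes. It also lists clinician time, per-clinic efficiency and a patient survey.

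The analysis sections describe the comparison differently:

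- SAP 9 will evaluate "differences between usual care and the intervention arm (intention to treat) in the receipt of active prescriptions for GDMT, hospitalizations, and mortality".
- SAP 9.2 tests each GDMT class with a "chi-squared test between intervention and usual care assignment".
- SAP 9.2 also plans a "Hazard ratio for heart failure hospitalization at final evaluation between intervention", where the line stops before naming a comparator. It gives no test for deaths.
- SAP 10 lists a mortality difference between intervention and usual care, without naming a population.

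The SAP contents list has entries 7.2.1 (intention to treat), 7.2.2 (per protocol) and 7.2.3 (safety). The body of 7.2 carries none of these subheadings.

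**The concern.** The same three outcome groups have two stated comparisons, one by assignment and one by receipt, and no rule says which governs. An analyst who takes the second paragraph of 7.2 as the rule would report prescriptions, hospitalizations and deaths from a contrast that randomization does not protect.

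Under SAP 5.1, only intervention patients are placed on clinic lists. Whether one of them has a telephone visit then depends on events after randomization: the clinician's discretion to call, apparent room to titrate, the patient answering and agreeing, and being alive on the clinic day. Each may be related to prognosis or to later prescribing.

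Study staff are not blinded to allocation (SAP 5.3). A choice between the two comparisons made after the data are seen would be hard to defend.

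**Working it through.** The plan gives no figure on this point, so there is none to reproduce. The check sets the sections side by side and then sizes what can be sized under stated assumptions.

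**1. Which outcomes conflict**

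- *GDMT classes:* by receipt in 7.2; by intention to treat in 9; by assignment in 9.2.
- *Hospitalizations:* by receipt in 7.2; by intention to treat in 9; comparator missing in 9.2.
- *Deaths:* by receipt in 7.2; by intention to treat in 9; no test in 9.2; difference between arms in 10.
- *Clinician time, clinic efficiency, survey:* not among the outcomes SAP 9 compares by arm, so no conflict.

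**2. Events before receipt.** SAP 7.2 keeps them in the primary analysis, but deaths and hospitalizations are only secondary outcomes. Either the phrase means the main intention-to-treat analysis of every outcome, or, read literally, it misses the outcomes it names. The text does not say which.

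**3. Who is compared depends on one phrase.** If the telephone intervention means a completed call, intervention patients with chart review only fall in neither group: they had a protocolized intervention but no call. SAP 5.1 expects such patients. If it means the whole programme, they count as recipients. Clinics run until every assigned patient has a review or an attempted call, so the groups are then close to the randomized arms, apart from deaths before review.

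**4. Survival to the clinic day, deaths only.** Assumptions, none stated in the documents: clinic time t uniform over a roll-out of W weeks, constant hazard, annual mortality r of 5-20%, no treatment effect, and deaths counted from randomization to W + 26 weeks. The documents give lists of 10 to 15 for 150 intervention patients, that is 150/15 = 10 to 150/10 = 15 clinics, without their spacing.

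With S(x) = (1 − r)^(x/52):

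- pre-clinic deaths = mean of 1 − S(t)
- usual care = 1 − S(W + 26)
- telephone group = 1 − S(W + 26) / mean of S(t)
- SE = √[(p₁(1 − p₁) + p₂(1 − p₂)) / 150]

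Example, W = 15 and r = 10%: usual care 1 − 0.9203 = 7.97%; pre-clinic deaths 1.50%; telephone group 1 − 0.9203/0.9850 = 6.57%. The ratio is 0.82 and the difference 1.40 points. SE = √[(0.0797 × 0.9203 + 0.0657 × 0.9343)/150] = 3.00 points, so the difference is 0.47 SE.

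| W (weeks) | Pre-clinic deaths | Usual care | Telephone | Ratio | Difference / SE |
|---|---|---|---|---|---|
| 2 | 0.10-0.43% | 2.72-11.32% | 2.63-10.94% | 0.97 | 0.05-0.10 |
| 5 | 0.25-1.07% | 3.01-12.46% | 2.77-11.51% | 0.92 | 0.12-0.25 |
| 10 | 0.49-2.12% | 3.49-14.31% | 3.01-12.46% | 0.86-0.87 | 0.23-0.47 |
| 15 | 0.74-3.15% | 3.96-16.13% | 3.25-13.41% | 0.82-0.83 | 0.33-0.67 |
| 30 | 1.47-6.17% | 5.37-21.36% | 3.97-16.19% | 0.74-0.76 | 0.58-1.15 |

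The most adverse placement counts deaths before review in the comparator. In the example this gives (0.0797 + 0.0150)/1.0150 = 9.33%, a ratio of 0.70 and a difference of 2.76 points, about 0.9 SE.

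**5. Hospitalizations.** Guaranteed survival to the clinic day also lengthens time at risk. Under the same assumptions, the telephone group has 0.1-2.8% more person-time for W = 2 to 15. At a constant admission rate this works against the intervention, so the net direction for total admissions is not established.

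**6. Precision, completed-call reading only.** If 40-70% of the 150 are reached (assumed), n = 60 to 105, so 90 to 45 patients leave the comparison. The SE changes by √(1/n + 1/150) / √(2/150), which is 1.32 at n = 60 and 1.10 at n = 105.

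**The case against.** The strongest reply is that the SAP already settles the matter. SAP 9 names intention to treat for exactly these three outcome groups, 9.2 repeats assignment for GDMT classes, and SAP 10 treats mortality by arm. The contents list puts a per-protocol population directly after the intention-to-treat one, and the two paragraphs of 7.2 follow that order. The sentence also cannot literally govern every secondary outcome, because clinician time, clinic efficiency and the survey belong to the intervention clinics. Finally, SAP 5.1 uses telephone/telemedicine panel management clinics as the name of the whole intervention, so the by-receipt groups may be almost the randomized arms.

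Most of this stands, and it limits the point. A reader might infer that the SAP abandons intention to treat for its secondary outcomes; SAP 9 says otherwise. A reader might infer that chart-review-only patients are dropped and that precision falls by 10-32%; that follows only from the completed-call reading and an assumed reach. A reader might infer that the secondary results would be biased towards the intervention. Only the survival component for deaths has a known direction; the documents do not establish one for hospitalizations or prescriptions.

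The reply does not remove the conflict itself. The 7.2 sentence is worded as the rule for the secondary outcomes assessment and carries no label. SAP 9 does not say that it overrides 7.2, and the hazard-ratio line that could confirm the comparison for hospitalization is unfinished.

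**Conclusion.** The conflict between SAP 7.2 and SAP 9 is real and should be resolved before outcome data are examined. It concerns GDMT classes, hospitalizations and deaths. A per-protocol intent is the likely explanation, but the text does not state it.

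The size of the selection bias cannot be computed from the documents. The survival component for deaths, measured against usual care, is small relative to sampling error for roll-outs up to 15 weeks (at most 0.67 SE). It is larger for a 30-week roll-out, or if deaths before review are counted in the comparator. All of these figures rest on assumed roll-out, mortality and uniform clinic timing. The argument for the change is therefore the ambiguous rule, not a demonstrated large bias. The primary OPS analysis is not affected.

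**What to change.** Four wording changes to the SAP:

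1. In 7.2, state that GDMT classes, hospitalizations and deaths are compared by randomized assignment in all randomized patients, as in SAP 9.
2. In 7.2, state that events before receipt of the intervention are included in these secondary analyses, and name the starting point for counting in both arms. SAP 9 gives no time origin.
3. In 9.2, complete the hazard-ratio line by adding the words: and usual care assignment.
4. Label the by-receipt contrast per-protocol and supplementary, define the telephone intervention, and say where chart-review-only patients and deaths before review belong.

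Clinician time, clinic efficiency and survey outcomes need no change.

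Cost: the by-receipt contrast loses any standing as a main analysis. Some chart abstraction may also be needed. The dashboard reports hospitalizations over the past 12 months (SAP 5.4 and Table 2). If randomization falls at the start of a roll-out of W weeks, an export at W + 26 weeks looks back 52 − (W + 26) = 26 − W weeks before randomization: 24 weeks for W = 2 and 11 for W = 15. Admissions from before randomization would have to be separated out, whereas a roll-out longer than 26 weeks would leave early follow-up uncovered.
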